7.7.6 Secondary Safety Analysis

Safety outcomes will include the proportion of patients with SAEs (including with fatal outcome) as well as the nature of SAEs as classified by Medical Dictionary for Regulatory Activities (MedDRA) preferred term (PT) and system organ class (SOC). For the analysis of safety, patients will be considered as treated for up to 90 days after discontinuation of therapy or 30 days after a treatment switch.

An overall summary table of all SAEs will be presented with the number and proportion of patients and the number of events, number and proportion of SAEs with fatal outcome, and number and proportion of SAEs that led to study treatment discontinuation. Additionally, the SAEs will be summarized by number and proportion of SAEs by PT and SOC.

Listings of all reportable AEs (including special situations), and product quality complaints (PQCs) reported in accordance with pharmacovigilance requirements (Section 9) will also be included in the final study report.

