6.2 Secondary Objectives

- 1. Among all new users of belzutifan¹, to describe:
 - a. Proportion of patients with treatment emergent SAEs, including the nature of these events.
 - b. Treatment patterns including the:
 - i. Duration of therapy
 - ii. Proportion of patients who discontinued treatment, time to treatment discontinuation, and summary of reasons for discontinuation
 - iii. Proportion of patients who interrupted treatment, time to treatment interruption, duration of treatment interruption, and summary of reasons for treatment interruption
 - iv. Proportion of patients with dose reductions, and reason for dose reduction.
- 2. Among new users of belzutifan with VHL disease-associated RCC and, separately, VHL disease-associated CNS hemangioblastoma, to describe:
 - a. Proportion of patients who develop metastatic disease (for RCC only)
 - b. Proportion of patients with occurrence of new VHL disease-associated tumor or tumor type

¹ see Section 7.2.1. (Inclusion Criteria). Depending on the approved local label, this may include patients with VHL disease-associated RCC, CNS hemangioblastoma, or pNET.

PRODUCT: MK-6482	PROTOCOL/AMENDMENT VERSION NO.: 6482-026/3.0
REVOPS ID NO: NIS102327	CORE DRC APPROVAL DATE: 28-NOV-2023
EPIDEMIOLOGY NO. (PE STUDIES ONLY): EP05047.006	CRC PRC APPROVAL DATE: N/A

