Patients will be followed from enrollment and treatment until the end of observation, defined as the earliest of withdrawal of consent, loss to follow-up, death, or until the end of the study. The planned minimum follow-up for each patient will be 3 years, noting that with a median duration of treatment follow-up of 2.4 years in the pivotal trial (MK-6482-004)², the majority of surgeries and reports of disease progression occurred within ~3 years of treatment, and the highest exposure-adjusted event rate occurred within 3 months of treatment. The non-interventional study duration considers the feasibility of running a long-term prospective observational cohort study while maintaining scientifically robust assessments. With a planned enrollment of patients within 2-3 years, the planned maximum follow-up for patients in the registry will be up to 5-6 years.

Up to 100 patients with VHL disease-associated RCC, CNS hemangioblastoma or pNET will be enrolled in the registry. This includes approximately 40 patients with VHL disease-associated RCC and approximately 40 patients with VHL disease-associated CNS

² 15-Jul-2021 database lock

	2
PRODUCT: MK-6482	PROTOCOL/AMENDMENT VERSION NO.: 6482-026/3.0
REVOPS ID NO: NIS102327	CORE DRC APPROVAL DATE: 28-NOV-2023
EPIDEMIOLOGY NO. (PE STUDIES ONLY): EP05047.006	CRC PRC APPROVAL DATE: N/A

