7.2.1 Inclusion Criteria

Patients will be included if they meet the following criteria at the index date³:

- 1. ≥ 18 years of age.
- 2. Diagnosed with VHL disease based on a germline test or clinical diagnosis.
- 3. A decision has been made by the treating physician (at his/her discretion) to initiate the first belzutifan treatment (i.e., belzutifan 'new users'), within the prescribing conditions of the approved product label.
- 4. Signed informed consent prior to or within 30 days after the first initiation of belzutifan.

³ index date for the patient is defined as the date of first administration of belzutifan

PRODUCT: MK-6482	PROTOCOL/AMENDMENT VERSION NO.: 6482-026/3.0
REVOPS ID NO: NIS102327	CORE DRC APPROVAL DATE: 28-NOV-2023
EPIDEMIOLOGY NO. (PE STUDIES ONLY): EP05047.006	CRC PRC APPROVAL DATE: N/A

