7.7.1 General Consideration

All statistical analyses will be performed using Statistical Analysis System[®] (Cary, North Carolina version 9.4 or higher) unless otherwise stated. No formal statistical hypothesis testing will be performed, and all the analyses will be primarily descriptive in nature. When appropriate, and unless otherwise specified, 95% confidence intervals (CIs) will be displayed.

	3	31
PRODUCT: MK-6482	PROTOCOL/AMENDMENT VERSION NO.: 6482-026/3.0	
REVOPS ID NO: NIS102327	CORE DRC APPROVAL DATE: 28-NOV-2023	
EPIDEMIOLOGY NO. (PE STUDIES ONLY): EP05047.006	CRC PRC APPROVAL DATE: N/A	

A 95% exact binomial CI (based on Clopper and Pearson method) will be calculated for proportion outcomes (e.g., primary outcome proportion of patients who undergo surgery or locally directed therapy).

Descriptive statistics will include the number of available data, number of missing data and the following:

- Mean, standard deviation (SD), minimum, median, maximum, first and third quartiles and 95% CIs for means/medians.
- Counts and percentages of each category for categorical variables with 95% CIs.

Percentages will be based on the number of non-missing observations.

Missing data will not be replaced. Imputation rules will be detailed in the SAP, as appropriate (e.g., for incomplete dates).

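### Section 7.7.6 reports SAEs by PT and SOC, fatal SAEs and SAEs leading to discontinuation as shares of SAEs, although the safety objective is per patient

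*Protocol*

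**What the plan says.** Secondary objective 1a (Protocol, 6.2) is set per patient: "Proportion of patients with treatment emergent SAEs, including the nature of these events". Section 7.7.6 opens in the same unit: "Safety outcomes will include the proportion of patients with SAEs (including with fatal outcome) as well as the nature of SAEs", with nature classified by MedDRA PT and SOC.

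The tables are then described in two units. The overall table is per patient, with events counted beside it: "An overall summary table of all SAEs will be presented with the number and proportion of patients and the number of events". The remaining rows are per event: "number and proportion of SAEs with fatal outcome, and number and proportion of SAEs that led to study treatment discontinuation". The breakdown by type is also per event: "Additionally, the SAEs will be summarized by number and proportion of SAEs by PT and SOC".

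Section 7.7.1 sets the interval method for proportions: "A 95% exact binomial CI (based on Clopper and Pearson method) will be calculated for proportion outcomes". Section 7.7.2 defines the safety population as everyone given at least one dose. For safety, a patient counts as treated until 90 days after discontinuation or 30 days after a treatment switch (7.3.1, 7.7.6). Section 7.7 leaves detail and table templates to the SAP and allows the SAP to change this section.

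**The concern.** The objective and the first sentence of 7.7.6 ask how many patients are affected. The rows that describe which events occurred, which were fatal and which ended treatment are instead divided by the total number of SAEs. The effectiveness section (7.7.5) counts patients, so the event unit is peculiar to safety.

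A share of SAEs depends on how often events repeat within a patient and on how many unrelated SAEs are recorded. It can rise or fall with no change in the risk of the event in question. In a registry of up to 100 patients, one patient with recurrent events can move a PT row visibly. The per-term safety result would then not be a risk that a prescriber or regulator could use or set beside other data.

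A related, lesser point is that time at risk for SAEs differs between patients, because the window closes soon after treatment stops, and 7.7.6 states no person-time measure.

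**Working it through.** **Plan's own figures.** The protocol gives no size or precision figure for SAEs, so there is none to reproduce directly. Its interval method can be checked on Table 2 (section 7.5, n = 40). Clopper-Pearson limits are the 2.5% quantile of Beta(x, n-x+1) and the 97.5% quantile of Beta(x+1, n-x).
- 10% of 40, x = 4: 2.79% to 23.66% (Table 2: 2.8% to 23.7%).
- 8% of 40, x = 3.2: 1.80% to 21.05% (Table 2: 1.8% to 21.1%).

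The method matches the plan.

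**Event share against patient risk.** Inputs: N = 100, the registry's upper limit (7.5). The SAE counts are assumptions, because the documents give none.

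| Patients with the PT | SAEs of the PT | All SAEs | Share of SAEs | Patients affected (exact 95% CI) |
|---|---|---|---|---|
| 10 | 10 | 50 | 10/50 = 20% | 10/100 = 10% (4.9-17.6%) |
| 2 | 10 | 50 | 10/50 = 20% | 2/100 = 2% (0.2-7.0%) |
| 10 | 10 | 20 | 10/20 = 50% | 10/100 = 10% (4.9-17.6%) |
| 10 | 10 | 100 | 10/100 = 10% | 10/100 = 10% (4.9-17.6%) |

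Rows 1 and 2 have the same event share and a fivefold difference in patient risk. Rows 1, 3 and 4 have the same patient risk, while the event share runs from 10% to 50% because the number of other SAEs changes.

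**Interval on events.** If the 7.7.1 method were applied to 10 of 50 SAEs, it would give 10.0% to 33.7% in both row 1 and row 2. In row 2 the ten events come from two patients and are not ten independent observations, so the interval has no valid coverage there.

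**Fatal SAEs.** Two fatal SAEs, one in each of two patients, are 2/50 = 4% of SAEs but 2/100 = 2% of patients. Recurrence plays no part here; the denominator alone makes the difference.

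**Time at risk.** At a constant first-SAE rate r, the proportion with an SAE by time t is 1 - exp(-rt). The rates are assumed. The times are the planned minimum follow-up (3 years) and the upper end of the maximum (6 years), taken as time on treatment.
- r = 0.05 per patient-year: 13.9% at 3 years, 25.9% at 6 years.
- r = 0.10: 25.9% and 45.1%.
- r = 0.20: 45.1% and 69.9%.

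The crude proportion rises by a factor of about 1.5 to 1.9 with no change in hazard, so it needs a rate beside it to be read.

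**Late consent.** Consent may follow first dose by up to 30 days (7.2.1). Assume a rate of 0.10 per patient-year after month 3, a rate 3 or 5 times higher before it, and, as the worst case, that nobody with an SAE in days 0-30 enrols.
- 3 times: hazard in 30 days 0.3 x 30/365.25 = 0.0246. Three-year hazard 0.3 x 0.25 + 0.1 x 2.75 = 0.35. The 3-year proportion falls from 29.5% to 27.8%.
- 5 times: hazard in 30 days 0.0411, three-year hazard 0.40. The proportion falls from 33.0% to 30.2%.

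The loss is about 2 to 3 percentage points, an upper bound under these assumptions.

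**The case against.** The strongest reply has four parts.

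- **The objective is met.** It asks for a proportion of patients plus the nature of the events, and the overall table supplies that proportion with an exact interval. This stands. A reader might infer that the safety objective goes unanswered, but the documents do not support that. What is missing is a patient-level figure for each type of event.
- **Recurrence cannot dominate the fatal and discontinuation rows.** A patient dies once and normally stops treatment for good once. This stands for the numerators, which will be close to patient counts. The denominator is still all SAEs, so the percentage remains something other than a patient risk, and the first sentence of 7.7.6 promises a patient-level proportion that includes fatal outcome.
- **The SAP may settle it.** Section 7.7 allows that, and it is a good answer on person-time rates, whose absence from a protocol is no error in itself. It is weaker on the unit: here the protocol is not silent but names one that disagrees with its objective, and an SAP that follows the text repeats the mismatch.
- **Late consent is not a flaw in 7.7.6.** A reader might infer that a consent window of up to 30 days ("Signed informed consent prior to or within 30 days after the first initiation of belzutifan") materially biases early safety. The documents do not support this. Data collection is anchored at first dose and Table 1 collects SAEs at the index/enrollment visit, so early events in those who consent are captured. Only patients who die, or cannot or will not consent, are lost, and the worst case above is modest. Section 7.1 does say "the highest exposure-adjusted event rate occurred within 3 months of treatment", but it does not say that these events are SAEs, so it cannot be read as an early SAE peak.

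**Conclusion.** The point holds as a mismatch of unit. Section 7.7.6 fixes the PT/SOC summary and the fatal and discontinuation rows as proportions of SAEs, while objective 1a and the section's own opening sentence are per patient. Under the assumed counts, an identical 20% event share corresponds to a patient risk of 10% or 2%, and an exact binomial interval on events would not reflect repeat events within a patient. The true size depends on how SAEs cluster in the registry, which the documents do not allow anyone to predict.

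The overall patient proportion is already planned and needs no correction beyond a supporting rate. The matter is one of wording and table layout, worth correcting before the tables are built.

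**What to change.** In 7.7.6, state that the following are reported as number and percent of patients, with the safety population as denominator and exact 95% CIs:
- patients with at least one SAE, by SOC and by PT;
- patients with a fatal SAE;
- patients with an SAE leading to discontinuation of belzutifan.

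Keep the event counts in an adjacent column, without a binomial interval. Add an SAE rate per 100 patient-years as a supporting column, using the treated period that 7.7.6 already defines. Report the number of patients who consented after first dose as context only.

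The cost is a few extra table columns and a change of wording. Dosing, consent and SAE data are already collected under Table 1, so no new data item is needed.

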7.8 Quality Control

By signing this protocol, all parties agree to following applicable standard operating procedures (SOPs). All parties also agree to ensuring all existing and new study personnel are appropriately trained to ensure the study is conducted and data are generated, documented, and reported in compliance with the protocol, Good Pharmacoepidemiology Practice (GPP)⁹, and all applicable federal, state, and local laws, rules and regulations. All parties should maintain transparency and open communication in order to effectively manage the study and proactively mitigate any risks.

The Sponsor may conduct routine or for-cause audits to ensure oversight and conduct of the study are completed in accordance with the protocol, quality standards (e.g., GPP), and applicable laws and regulations. If a significant quality issue (SQI) is identified at any time during the conduct of the study, it must be escalated to the Sponsor immediately. A SQI is any issue with the potential to negatively impact, either directly or indirectly, the rights, safety and well-being of patients or study patients and/or the integrity of the data. In the event an audit or SQI results in corrective or preventive actions, all parties are expected to appropriately implement the action plan in a timely manner.

7.9 Limitations of the Research Methods

Limitations of this prospective observational cohort study and how they will be addressed are summarized in Table 3.

As this is a real-world study with patients treated under routine clinical practice, patients may be lost to follow-up. Those patients who are lost to follow-up may have different clinical and demographic characteristics than those who remain in the study leading to bias of the study results.

	34
PRODUCT: MK-6482	PROTOCOL/AMENDMENT VERSION NO.: 6482-026/3.0
REVOPS ID NO: NIS102327	CORE DRC APPROVAL DATE: 28-NOV-2023
EPIDEMIOLOGY NO. (PE STUDIES ONLY): EP05047.006	CRC PRC APPROVAL DATE: N/A

Potential Limitation	Description	Mitigation
Enrollment uncertainty	VHL is a rare disease with an evolving treatment landscape which may pose challenges in enrollment.	Feasibility assessments of sites will be performed to identify those sites with adequate projected patient counts. Enrollment will be closely monitored and extended to additional sites and countries, as required and feasible.
Selection bias	External validity: Patients who enroll in this study may not be generally representative of the overall VHL population (e.g., patients prescribed belzutifan may have different disease prognosis) Internal validity: As this is a real-world study with patients treated under routine clinical practice, patients may be lost to follow-up. Those patients who are lost to follow-up may have different clinical and demographic characteristics than those who remain in the study leading to bias of the study results.	Patients will be enrolled from different sites. An evaluation of patient clinical and demographic characteristics will inform the assessment of the extent of selection bias.
Unmeasured risk factors for study outcomes	There may be unmeasured clinical or demographic characteristics that are related to the study outcomes impacting the interpretation of the effectiveness or safety outcomes.	To the extent possible, known clinical and demographic factors related to the study outcome will be collected from the patients' medical record. If a clinically meaningful unmeasured factor is identified, the feasibility of sensitivity analyses to determine the impact will be explored.

Table 3Limitations of the Research Methods

	35
PRODUCT: MK-6482	PROTOCOL/AMENDMENT VERSION NO.: 6482-026/3.0
REVOPS ID NO: NIS102327	CORE DRC APPROVAL DATE: 28-NOV-2023
EPIDEMIOLOGY NO. (PE STUDIES ONLY): EP05047.006	CRC PRC APPROVAL DATE: N/A

Potential Limitation	Description	Mitigation
Lack of internal comparator	The study will enroll only patients receiving belzutifan, leading to the inability to place into context the outcome assessments.	External information from other studies in this population (e.g., natural history study of VHL) will be used to provide context around study estimates and findings.
	Comparison of the efficacy of belzutifan with other treatment modalities will not be performed as differences in measured and unmeasured prognostic variables between the treatment groups would likely render any comparison of treatment effectiveness or safety invalid in a non-randomized setting.	
Generalizabl e results	Given differences in the indication statement, results may not be generalizable.	As the approved indication statement for belzutifan may differ between countries included in the study, subgroup analyses will be performed, as relevant, for countries with different indication statements.
Information bias	Study assessments will be obtained through the patients' medical record and may not be verified against a gold standard leading to misclassification.	The data collected will include as much detail as is available within each patient's record, including but not limited, to histopathologic results, and relevant laboratory and imaging results.

VHL=Von Hippel-Lindau

PRODUCT: MK-6482	PROTOCOL/AMENDMENT VERSION NO.: 6482-026/3.0
REVOPS ID NO: NIS102327	CORE DRC APPROVAL DATE: 28-NOV-2023
EPIDEMIOLOGY NO. (PE STUDIES ONLY): EP05047.006	CRC PRC APPROVAL DATE: N/A

8 **PROTECTION OF HUMAN SUBJECTS**

8.1 Informed Consent

Consent must be documented by the patient's dated signature or by the patient's legally acceptable representative's dated signature on a consent form along with the dated signature of the person conducting the consent discussion.

A copy of the signed and dated consent form should be given to the patient before participation in the study.

The initial informed consent form, any subsequent revised written informed consent form and any written information provided to the patient must receive the IRB/IEC's approval/favorable opinion in advance of use. The patient or his/her legally acceptable representative should be informed in a timely manner if new information becomes available that may be relevant to the patient's willingness to continue participation in the study. The communication of this information will be provided and documented via a revised consent form or addendum to the original consent form that captures the patient's dated signature or by the patient's legally acceptable representative's dated signature.

Specifics about a study and the study population will be added to the consent form template.

The informed consent will adhere to IRB/IEC requirements, applicable laws and regulations and Sponsor requirements.

Additionally, age (in years) and sex for patients approached but who do not consent to participate in the study and reason(s) for not participating may be collected if agreed by IRBs/IECs.

8.1.1 Consent and Collection of Specimens for Future Biomedical Research

Not applicable; the study does not involve specimen collection.

PRODUCT: MK-6482	PROTOCOL/AMENDMENT VERSION NO.: 6482-026/3.0
REVOPS ID NO: NIS102327	CORE DRC APPROVAL DATE: 28-NOV-2023
EPIDEMIOLOGY NO. (PE STUDIES ONLY): EP05047.006	CRC PRC APPROVAL DATE: N/A

9 MANAGEMENT AND REPORTING OF ADVERSE EVENTS/ADVERSE REACTIONS

Adverse Event (AE) and Product Quality Complaint (PQC) Reporting Language for Non-Interventional Study Protocols

Introduction

This is a non-interventional study based on secondary use of data collected for other purposes. No administration of any therapeutic or prophylactic agent is required in this protocol, and there are no procedures required as part of this protocol.

9.1 Adverse Event and Product Quality Complaint Reporting

9.1.1 Investigator Responsibility

Although AEs and PQCs are not actively solicited in this study, there are certain circumstances in which individual AEs and/or PQCs will be reported. For example, during review of medical records or physicians notes (paper or electronic), to collect data as required by the protocol, if a notation of an AE* or PQC to belzutifan or any other Sponsor products as identified, the AE/PQC must be reported according to Table 4. If any health outcomes are described in Section 7.3.2, they must be assessed for AE reportability according to Table 4 (refer to Section 7.3.2 for more information).

*For the purposes of this protocol, the term "AE" for reporting outlined in Table 4 collectively refers to the following reportable events (refer to Section 9.2 for definitions):

- Serious adverse reactions (SARs), including death
- Non-serious adverse reactions (NSARs)
- Special situations

AEs, PQCs, and AEs that occur in combination with PQCs, or spontaneously reported events, should all be captured using the AE/PQC report form for each patient and reported according to Table 4.

	38
PRODUCT: MK-6482	PROTOCOL/AMENDMENT VERSION NO.: 6482-026/3.0
REVOPS ID NO: NIS102327	CORE DRC APPROVAL DATE: 28-NOV-2023
EPIDEMIOLOGY NO. (PE STUDIES ONLY): EP05047.006	CRC PRC APPROVAL DATE: N/A

Table 4 A	AE and PQC Reporting	Timeframes	and Process f	for Investigators	and Suppliers
-----------	----------------------	------------	---------------	-------------------	---------------

AEs and PQCs	Investigator Timeframes	Supplier Timeframes	
	Investigator to Supplier	Supplier to Sponsor [3]	
	[1], [2]		
SAR	24 hours from receipt	1 BD/3 CD from time of	
		receipt from investigator	
Serious Special Situations, regardless of causality			
NSAR	10 CD from receipt	10 CD from time of	
		receipt from investigator	
Non-serious Special Situation, regardless of causality			
PQC with or without an AE (SAR/NSAR/Special	24 hours from receipt	24 hours from time of	
situation)		receipt from investigator	
Follow-up to any AE/PQC-submit using above timeframes			
BD-Business Day; CD-Calendar Day			
Non-Sponsor Products: If the investigator elects to sub	mit AEs/PQCs for non-Spo	nsor products, they should	
be reported to the market authorization holder (MAH) for that product or to the health authority according to			
the institution's policy or local laws and regulations.			
